3.1 Inclusion Criteria

- 3.11 Age \geq 18 years.
- 3.12 Locally recurrent and unresectable and/or distant metastatic differentiated thyroid cancer (DTC), histologically or cytologically confirmed. The diagnosis of DTC includes the following subtypes: Papillary thyroid cancer (PTC) (including but not limited to variants such as follicular variant, tall cell, columnar cell, Hürthle cell variant of papillary carcinoma, and poorly differentiated), Follicular thyroid cancer (FTC), including Insular variant, Hürthle cell carcinoma and poorly differentiated thyroid cancer.
- 3.13 Measurable disease meeting the following criteria (see Section 11.0):
 - 3.13a At least 1 lesion of \geq 1.0 cm in the longest diameter for a non-lymph node or \geq 1.5 cm in the short-axis diameter for a lymph node which is

serially measurable according to RECIST 1.1 using computerized tomography/magnetic resonance imaging (CT/MRI). If there is only one target lesion and it is a non-lymph node, it should have a longest diameter of ≥ 1.5 cm.

- 3.13b. Lesions that have had external beam radiotherapy (EBRT) or loco-regional therapies such as radiofrequency (RF) ablation must show evidence of progressive disease based on RECIST 1.1 to be deemed a target lesion.
- 3.14 For Cohort 1 Only: Evidence of disease progression ≤ 14 months prior to registration according to RECIST 1.1, as confirmed by the site study PI.
- 3.15 For Cohort 2 Only: Progressive disease (PD) on lenvatinib per RECIST 1.1 ≤ 60 days prior to registration, as confirmed by the site study PI. Patients need to have documented imaging and measurement of RECIST target lesions within 30 days of starting pembrolizumab.
- 3.16 Radioiodine (RAI)-resistant disease as defined by one or more of the following criteria:
- a. One or more measurable lesions that do not demonstrate RAI uptake
 - b. One or more measurable lesions progressive by RECIST 1.1 ≤ 14 months of prior RAI therapy.
 - c. One or more measurable lesions present after cumulative RAI dose of ≥ 600 mCi.
 - d. One or more measurable lesions that are FDG-avid (>5 SUV), if PET/CT scan performed. These lesions may also be RAI-avid.
- 3.17 ECOG Performance Status (PS) 0 or 1. (Form is available on the ACCRU web site)

- 3.18 The following laboratory values obtained ≤ 30 days prior to registration, unless otherwise specified:

System	Laboratory Value
Hematological	
Absolute neutrophil count (ANC)	$\geq 1,500$ /mcL
Platelets	$\geq 100,000$ / mcL

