- 9.6 Apart from the assigned study drugs, subjects are **prohibited from receiving the following therapies** during the Screening and Treatment Phase (including retreatment for post-complete response relapse) of this trial:
- 9.61 Antineoplastic systemic chemotherapy or biological therapy
 - 9.62 Immunotherapy not specified in this protocol
 - 9.63 Chemotherapy not specified in this protocol
 - 9.64 Investigational agents other than pembrolizumab and lenvatinib
 - 9.65 Radiation therapy. NOTE: Radiation therapy to a symptomatic solitary lesion or to the brain may be allowed at the investigator's discretion.
 - 9.66 Live vaccines within 30 days prior to the first dose of trial treatment and while participating in the trial. Examples of live vaccines include, but are not limited to, the following: measles, mumps, rubella, varicella/zoster, yellow fever, rabies, BCG, and typhoid vaccine.

- 9.67 Systemic glucocorticoids for any purpose other than to modulate symptoms from an event of clinical interest of suspected immunologic etiology. The use of physiologic doses of corticosteroids may be approved after consultation with the ACCRU Quality Assurance Specialist (see protocol resource page).
- 9.68 Subjects who, in the assessment by the investigator, require the use of any of the aforementioned treatments for clinical management should be removed from the trial. Subjects may receive other medications that the investigator deems to be medically necessary.

The Exclusion Criteria describes other medications which are prohibited in this trial.

There are no prohibited therapies during the Post-Treatment Follow-up Phase.

9.7 Pneumonitis:

For **Grade 2 events**, treat with systemic corticosteroids. When symptoms improve to Grade 1 or less, steroid taper should be started and continued over no less than 4 weeks.

For **Grade 3-4 events**, immediately treat with intravenous steroids. Administer additional antiinflammatory measures, as needed. Add prophylactic antibiotics for opportunistic infections in the case of prolonged steroid administration.

9.8 Type 1 Diabetes Mellitus (if new onset, including diabetic ketoacidosis [DKA]) or Grade 3 Hyperglycemia, if associated with ketosis (ketonuria) or metabolic acidosis (DKA)

For **T1DM** or **Grade 3-4 Hyperglycemia**

- Insulin replacement therapy is recommended for Type I diabetes mellitus and for Grade 3-4 hyperglycemia associated with metabolic acidosis or ketonuria.

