11.2 Definitions of Measurable and Non-Measurable Disease

11.21 Measurable Disease

11.211 A non-nodal lesion is considered measurable if its longest diameter can be accurately measured as ≥ 1.0 cm with CT scan, CT component of a PET/CT, or MRI.

11.212 A superficial non-nodal lesion is measurable if its longest diameter is ≥ 1.0 cm in diameter as assessed using calipers (e.g. skin nodules) or imaging. In the case of skin lesions, documentation by color photography, including a ruler to estimate the size of the lesion, is recommended.

11.213 A malignant lymph node is considered measurable if its short axis is ≥ 1.5 cm when assessed by CT scan (CT scan slice thickness recommended to be no greater than 5 mm).

NOTE: Tumor lesions in a previously irradiated area are not considered measurable disease.

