11.4 Measurement of Effect

11.41 Target Lesions & Target Lymph Nodes

- Measurable lesions (as defined in Section 11.21) up to a maximum of 5 lesions, representative of all involved organs, should be identified as “Target Lesions” and recorded and measured at baseline. These lesions can be non-nodal or nodal (as defined in 11.21), where no more than 2 lesions are from the same organ and no more than 2 malignant nodal lesions are selected.

Note: If fewer than 5 target lesions and target lymph nodes are identified (as there often will be), there is no reason to perform additional studies beyond those specified in the protocol to discover new lesions.

- Target lesions and target lymph nodes should be selected on the basis of their size, be representative of all involved sites of disease, but in addition should be those that lend themselves to reproducible repeated measurements. It may be the case that, on occasion, the largest lesion (or malignant lymph node) does not lend itself to reproducible measurements in which circumstance the next largest lesion (or malignant lymph node) which can be measured reproducibly should be selected.
- Baseline Sum of Dimensions (BSD): A sum of the longest diameter for all target lesions plus the sum of the short axis of all the target lymph nodes will be calculated and reported as the baseline sum of dimensions (BSD). The BSD will be used as reference to further characterize any objective tumor response in the measurable dimension of the disease.
- Post-Baseline Sum of the Dimensions (PBSD): A sum of the longest diameter for all target lesions plus the sum of the short axis of all the target lymph nodes will be calculated and reported as the post-baseline sum of dimensions (PBSD). If the radiologist is able to provide an actual measure for the target lesion (or target lymph node), that should be recorded, even if it is below 0.5 cm. If the target lesion (or target lymph node) is believed to be present and is faintly seen but too small to measure, a default value of 0.5 cm should be assigned. If it is the opinion of the radiologist that the target lesion or target lymph node has likely disappeared, the measurement should be recorded as 0 cm.
- The minimum sum of the dimensions (MSD) is the minimum of the BSD and the PBSD.

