11.43 Response Criteria

- 11.431 All target lesions and target lymph nodes followed by CT/MRI/PET-CT/Chest X-ray/physical examination must be measured on re-evaluation at evaluation times specified in Section 11.1. Specifically, a change in objective status to either a PR or CR cannot be done without re-measuring target lesions and target lymph nodes.

Note: Non-target lesions and non-target lymph nodes should be

evaluated at each assessment, especially in the case of first response or confirmation of response. In selected circumstances, certain non-target organs may be evaluated less frequently. For example, bone scans may need to be repeated only when complete response is identified in target disease or when progression in bone is suspected.

11.432 Evaluation of Target Lesions

- Complete Response (CR): All of the following must be true:
 - a. Disappearance of all target lesions.
 - b. Each target lymph node must have reduction in short axis to <1.0 cm.
- Partial Response (PR): At least a 30% decrease in PBSD (sum of the longest diameter for all target lesions plus the sum of the short axis of all the target lymph nodes at current evaluation) taking as reference the BSD (*see* Section 11.41).
- Progression (PD): At least one of the following must be true:
 - a. At least one new malignant lesion, which also includes any lymph node that was normal at baseline (< 1.0 cm short axis) and increased to ≥ 1.0 cm short axis during follow-up.
 - b. At least a 20% increase in PBSD (sum of the longest diameter for all target lesions plus the sum of the short axis of all the target lymph nodes at current evaluation) taking as reference the MSD (Section 11.41). In addition, the PBSD must also demonstrate an absolute increase of at least 0.5 cm from the MSD.
 - c. See Section 11.32 for details in regards to the requirements for PD via FDG-PET imaging.
- Stable Disease (SD): Neither sufficient shrinkage to qualify for PR, nor sufficient increase to qualify for PD taking as reference the MSD.

11.433 Evaluation of Non-Target Lesions & Non-target Lymph Nodes

- Complete Response (CR): All of the following must be true:
 - a. Disappearance of all non-target lesions.
 - b. Each non-target lymph node must have a reduction in short axis to <1.0 cm.
- Non-CR/Non-PD: Persistence of one or more non-target lesions or non-target lymph nodes.
- Progression (PD): At least one of the following must be true:

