13.0 Treatment/Follow-up Decision at Evaluation of Patient

- 13.1 Patients who are CR, PR, or SD will continue treatment per protocol.
- 13.2 Patients who develop PD while receiving therapy or refuse treatment or choose alternative therapy will go to the event-monitoring phase per Section 18.0 and be followed every 180 days for a maximum of 3 years from study registration. (See exceptions in 13.5 and 13.6.)
- 13.3 Patients who go off protocol treatment for reasons other than those listed in Section 13.2 above (e.g., adverse events, other complicating disease) will go to Observation and will follow the test schedule (Section 4.0) every 84 days for a maximum of 3 years from study registration. If they progress or choose alternative therapy while in Observation, they will go to the event-monitoring phase.
- 13.4 OBSERVATION: The study treatment period is 54 weeks (19 cycles). Patients who are receiving clinical benefit (i.e., in CR or PR or SD) and who are tolerating treatment at the end of the study treatment period may continue on therapy for an additional 12 months. After study treatment has been discontinued, they should be observed every 12 weeks until PD or a maximum follow-up of 3 years from study registration. Once the patient has PD during observation, they will be followed in the event-monitoring phase for a maximum follow-up of 3 years from study registration (see Section 18.0). Subsequent treatment is at the discretion of their attending physician. NOTE: If the patient continues for an additional 12 months of treatment beyond the initial 54 weeks, the patient should follow the same test schedule, per protocol, as is done during the initial 54-week period.
- 13.5 Patients who develop PD in the CNS may receive radiotherapy and continue treatment on study after completion of radiotherapy. **NOTE: Both lenvatinib and pembrolizumab should be withheld for a minimum of 3 days prior to radiation and for 3 weeks after radiation.**

13.6 Accumulating evidence indicates a minority of patients treated with immunotherapy may derive clinical benefit despite initial evidence of PD. Patients receiving treatment in this study will be permitted to continue treatment beyond initial PD, if the initial PD happens in the first 12 weeks post-registration (by RECIST 1.1), as long as they meet the following criteria:

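### Radiotherapy to a solitary lesion is permitted on study, but no rule says how that lesion is then scored, so a radiotherapy effect can count as a PR or, more rarely, a CR.

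*Combined protocol and SAP*

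**What the plan says.** **Radiotherapy on study.** Section 9.65 prohibits radiotherapy during screening and treatment, with this note, which leaves the decision to the investigator: "Radiation therapy to a symptomatic solitary lesion or to the brain may be allowed". Section 9.68 then says that subjects who "require the use of any of the aforementioned treatments for clinical management should be removed from the trial". Section 13.5 adds: "Patients who develop PD in the CNS may receive radiotherapy and continue treatment on study after completion of radiotherapy". Section 7.7 gives a similar provision for progression confined to the CNS.

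**Response scoring.** Under 11.41, measurable lesions "should be identified as “Target Lesions” and recorded and measured at baseline". Section 11.431 requires all target lesions to be re-measured at each scheduled evaluation. In 11.432 the target-lesion CR criterion is "Disappearance of all target lesions", with target nodes below 1.0 cm, and PR is a fall of at least 30% in the sum of dimensions from baseline. The 11.44 table combines target status, non-target status and new disease. It has no entry for a lesion irradiated on study.

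**Irradiated lesions.** The note in 11.21 says: "Tumor lesions in a previously irradiated area are not considered measurable disease". Section 3.13b says that lesions with prior external beam radiotherapy "must show evidence of progressive disease based on RECIST 1.1 to be deemed a target lesion".

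**Analysis.** Sections 16.12 and 16.14 count every eligible, consented, treated patient as evaluable and do not mention radiotherapy. Cohort 1 needs at least 2 CRs in 25. Cohort 2 stops if there are 0 confirmed responses in the first 15 patients and otherwise needs at least 4 in 25.

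**The concern.** The primary endpoints are meant to measure the effect of the drug combination. The response rules look only at size, so they cannot separate shrinkage due to the drugs from shrinkage due to radiotherapy. Confirmation at least 4 weeks later does not separate them either, because a lasting radiotherapy effect passes it.

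Both cohorts are single-arm, so no comparison group would reveal the problem. The decision rules also turn on very few events. One misattributed CR is half of what Cohort 1 needs. One misattributed response among the first 15 Cohort 2 patients passes the stage 1 rule by itself.

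**Working it through.** **Step 1: when the rules produce a success after radiotherapy**

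- *PR.* The irradiated lesion must be a target lesion, and its shrinkage must carry the sum of dimensions to a 30% fall. There must be no new lesions and no progression elsewhere. If confirmed, this is a Cohort 2 success.
- *CR.* Under 11.44 all target disease must be CR, all non-target disease must be CR, and there must be no new lesions. Radiotherapy to one lesion meets this only if that lesion is the only disease or the last that remains. Section 3.13a does admit patients with a single target lesion. However, bone lesions, effusions and small pathological nodes are non-target under 11.22 and 11.42, so a single target lesion need not be the only disease.
- *Non-target lesion.* Irradiating the last remaining non-target lesion can turn a drug PR into a CR.

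**Step 2: reproduce the plan's figures (exact binomial)**

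Cohort 1, at least 2 of 25:

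- P(go) = 1 − (1−p)^25 − 25p(1−p)^24
- p = 0.02: 1 − 0.6035 − 0.3079 = 0.0886 (stated 0.09)
- p = 0.15: 0.907 (stated 91%)

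Cohort 2, with X1 ~ Bin(15, p) and X2 ~ Bin(10, p):

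- P(go) = Σ over x = 1 to 15 of P(X1 = x) · P(X2 ≥ max(0, 4−x))
- p = 0.05: 0.0336 (stated 0.05, consistent as a ceiling)
- p = 0.25: 0.901 (stated 90%)

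The design figures stand.

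**Step 3: add radiotherapy-driven responses**

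Let q be the chance that a patient has a success due to radiotherapy, independently of drug response. The success probability under the null becomes p0 + (1−p0)q. The documents give no value for q, so 1%, 2% and 4% are assumptions. They correspond to about 0.25, 0.5 and 1 patient in 25.

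| Assumed q | Cohort 1 success prob. | Cohort 1 P(go) | Cohort 2 success prob. | Cohort 2 P(go) |
|---|---|---|---|---|
| 0 | 0.0200 | 0.089 | 0.0500 | 0.034 |
| 1% | 0.0298 | 0.170 | 0.0595 | 0.057 |
| 2% | 0.0396 | 0.260 | 0.0690 | 0.089 |
| 4% | 0.0592 | 0.440 | 0.0880 | 0.171 |

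**Step 4: exactly one such response (assumption), the other 24 patients at the null rate**

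- Cohort 1: at least 1 CR is needed among 24, so 1 − 0.98^24 = 0.384.
- Cohort 2, response among the first 15: stage 1 is passed and at least 3 of 24 are needed, so 0.116.
- Cohort 2, response among the last 10: stage 1 must also be passed by the other patients, so 0.112.

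**The case against.** **The 11.21 note may already cover this.** It is not expressly limited to baseline. A reader could apply it once a target lesion has been irradiated, call the target set not fully evaluated, and reach Not Evaluated in 11.44. Against that, the note sits in the definition used to select lesions, 11.431 still requires re-measurement, and 3.13b accepts an irradiated lesion that has progressed as a target. The note is ambiguous. It cannot be dismissed as irrelevant, but it cannot be relied on as a safeguard.

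**Section 9.68 may remove the patient.** If it governs, the on-study pathway narrows. But the 9.65 note reads as a specific exception, and 7.7 and 13.5 keep patients on treatment after CNS radiotherapy. Removal would not clearly end scoring either. Section 13.3 sends some patients who stop treatment to Observation, where the 18.1 timetable still collects RECIST measurements. The documents do not say whether radiotherapy counts as alternative therapy, which would instead send the patient to event monitoring.

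**The CR route is narrow.** This stands. A reader might infer that any patient whose only target lesion disappears after irradiation becomes a CR. The documents do not support that: with persisting non-target disease, 11.44 gives PR. The more plausible route is a PR in Cohort 2.

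**The magnitudes rest on assumption.** This also stands. The 0.384 would follow from any one misclassified CR, so it describes how sensitive the 2-of-25 rule is. It does not measure how often radiotherapy would cause the error. A reader might take it as the trial's actual false-positive rate, but the documents give no frequency of on-study radiotherapy or of response after it.

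**Conclusion.** The concern holds in limited form. As written, the rules can credit a radiotherapy effect to the drugs: as a PR in Cohort 2, and as a CR in Cohort 1 only when the irradiated lesion is the sole or last remaining disease. The stated power and significance levels are not in dispute.

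Under assumed rates of 1% to 4%, the false-positive rate rises from 0.089 to between 0.170 and 0.440 in Cohort 1, and from 0.034 to between 0.057 and 0.171 in Cohort 2. The same rates are applied to both cohorts for illustration only. Because a CR needs all disease to clear, the true rate in Cohort 1 is probably at the low end or below it. Section 9.65 does not define a solitary lesion, so the number of patients exposed cannot be estimated.

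A reader might conclude that no response after any radiotherapy should count. That goes too far. A patient irradiated to the brain may continue under 7.7 and 13.5, and a response in unirradiated lesions is still evidence about the drugs. The gap deserves closing because it is cheap to close and the decisions rest on so few events.

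**What to change.** Add to 11.43, and refer to it in 16.12 and 16.14:

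> A lesion irradiated on study is not evaluable for response from the start of radiotherapy. A CR or PR first met after radiotherapy that depends on the irradiated lesion is not a success for the primary endpoint. The patient stays in the denominator and PD still counts. A response still counts if it is met on the unirradiated lesions without relying on shrinkage of the irradiated lesion, or if it was met before radiotherapy and is confirmed on the unirradiated lesions.

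Add a matching footnote to the 11.44 table, so that its Not Evaluated row does not override the last sentence. One workable convention is to hold the irradiated lesion at its last size before radiotherapy when the sum is calculated for response.

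Record the date and site of on-study radiotherapy on the existing treatment or concomitant-medication forms. The only radiation form in the 18.1 timetable covers prior radiation.

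Reconcile 9.65 with 9.68 and with 7.7 and 13.5, and the 11.21 note with 3.13b. None of this need change who may receive radiotherapy.

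The cost is a few sentences and two data fields. The downside is that some true drug responses, visible only with the irradiated lesion included, will not be counted.

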10.0 Adverse Event (AE) Reporting and Monitoring

The site principal investigator is responsible for reporting any/all serious adverse events to the sponsor as described within the protocol, regardless of attribution to study agent or treatment procedure.

The sponsor/sponsor-investigator is responsible for notifying FDA and all participating investigators in a written safety report of any of the following:

- Any suspected adverse reaction that is both serious and unexpected.
- Any findings from laboratory animal or *in vitro* testing that suggest a significant risk for human subjects, including reports of mutagenicity, teratogenicity, or carcinogenicity.

- Any findings from epidemiological studies, pooled analysis of multiple studies, or clinical studies, whether or not conducted under an IND and whether or not conducted by the sponsor, that suggest a significant risk in humans exposed to the drug.
- Any clinically important increase in the rate of a serious suspected adverse reaction over the rate stated in the protocol or Investigator's Brochure (IB).

Definitions

Adverse Event

Any untoward medical occurrence associated with the use of a drug in humans, whether or not considered drug related.

Suspected Adverse Reaction

Any adverse event for which there is a reasonable possibility that the drug caused the adverse event.

Expedited Reporting

Events reported to sponsor within 24 hours, 5 days or 10 days of study team becoming aware of the event.

Routine Reporting

Events reported to sponsor via case report forms

Events of Interest

Events that would not typically be considered to meet the criteria for expedited reporting, but that for a specific protocol are being reported via expedited means in order to facilitate the review of safety data (may be requested by the FDA or the sponsor).

10.1 Adverse Event Characteristics

CTCAE term (AE description) and grade: The descriptions and grading scales found in the revised NCI Common Terminology Criteria for Adverse Events (CTCAE) version 4.0 will be used for AE reporting. All appropriate treatment areas should have access to a copy of the CTCAE version 4.0. A copy of the CTCAE version 4.0 can be downloaded from the CTEP web site:

- a. Adverse event monitoring and reporting is a routine part of every clinical trial.
- b. Identify the grade and severity of the event using the CTCAE version 4.0.
- c. Determine whether the event is expected or unexpected (see Section 10.2).
- d. Determine if the adverse event is related to the study intervention (agent, treatment or procedure) (see Section 10.3).
- e. Determine whether the event must be reported as an expedited report. If yes, determine the timeframe/mechanism (see Section 10.4).

- f. Determine if other reporting is required (see Section 10.5).
- g. Note: All AEs reported via expedited mechanisms must also be reported via the routine data reporting mechanisms defined by the protocol (see Sections 10.6 and 18.0).

Each CTCAE term in the current version is a unique representation of a specific event used for medical documentation and scientific analysis and is a single MedDRA Lowest Level Term (LLT).

NOTE: A severe AE, as defined by the above grading scale, is NOT the same as serious AE which is defined in the table in Section 10.4.

